## **Study Protocol**

After passing initial screening participants will attend a single study visit. Written informed consent will be provided either during the visit, or prior to the visit via the telephone or an internet meeting (e.g. Zoom). If consent is performed prior to the visit, the study team will either send a paper copy of the consent to the potential participant or provide a REDCap link to a REDCap for with the consent downloadable one week before the visit. If the participant chooses to have a paper copy mailed, the staff member will perform consenting as usual over the phone or internet and the participant will return the consent to the staff before or at the visit. If the potential participant chooses to receive an email link, the staff member will perform

consenting as usual over the phone and the participant will electronically sign the REDCap form using a signature box.

Strict timing of the protocol is necessary to capture response to acute exercise for CBF [ASL] (Table 1). ASL measures are time-sensitive and have been planned based on prior work.

Table 1. Steps in the Protocol are Highly Time-dependent (Exercise warm-up start begins timing [T0])

Time
1. Staff conduct informed consent and MRI safety screen. Then the participant changes into approved MRI compliant clothing.
2. Cognitive tests are administered on an iPad. Some participants who have not had a recent Clinical Cohort evaluation may be required to complete additional paper based cognitive assessments (~20 minutes) to index cognitive function.
3. The participant is escorted to the MRI suite, situated on the imaging table and a baseline scanning is performed for about 20 minutes.
4. Vitals are taken. A catheter is placed in the antecubital or other appropriate vein for ~10mL blood draw (if participant declines or is unable, repeated sticks may be used). An additional ~6mL blood draw will be taken for those not previously genotyped.
5. The participant moves to the space with exercise device. Seat height is adjusted, and participant is familiarized with device and cadence.
6. The participant works at a certain cadence and resistance according to an algorithm for a 2 min warm-up.  Then, staff increases workload incrementally over 3 min to reach 65-75% of age predicted heart rate maximum (APHRmax).
7. The participant maintains cadence while study staff titrate workload to maintain 65-75% APHRmax for 15 min. After 15 min, ~10mL blood and vitals are taken immediately. The participant cools-down self-selected cadence and low load for 3 min.
8. The participant returns to the MRI table. We have allotted 8 minutes for repositioning understanding that this population may need additional time to maximize comfort.
9. At time T36, additional MRI sequences in succession are acquired. Scan time is approximately 24 minutes
10. At time T60, participants return to the testing room for cognitive testing and ~10mL blood draw and vitals.

**Exercise Dose:** Several different aerobic workloads (from ~50% to 100% of maximum capacity and durations (15 minutes to 4 hours) have been used in prior studies of response to acute exercise. Our experience informs the selected exercise parameters as achievable by older adults.

Participants will exercise for 15 minutes at 65-75% of age-predicted heart rate maximum (APHRmax) calculated as  $208 - 0.7 \times \text{Age}$  or 220 minus age to be determined by tester based on medications, age, and perceived fitness level. We will use either an electronically braked cycle ergometer (Lode, Groningen, Nederland) or a NuStep recumbent stepper (NuStep, Ann Arbor, MI) to maintain precise control over workload and heart rate. We will also a small amount of water as needed after exercise to account for any dehydration that might affect blood volume measured by MRI.

**Blood Draw:** Following catheter placement prior to exercise, blood (~10mL) will be drawn into a serum-separating vacutainer tube. An identical blood draw will be performed immediately after exercise and after post-exercise cognitive testing. Serum will be processed and frozen at -80C until further analysis using colorimetric ELISA for our identified blood-based biomarkers. Some blood will be banked for future analysis.

Blood draws will be performed at Hoglund by appropriately trained staff. If the participant has not previously been genotyped as part of a KU ADC study, an additional ~6mL of blood will be drawn at baseline for the purposes of genotyping.

**Imaging Parameters:** The investigative team has extensive experience with imaging and preliminary evidence to demonstrate the necessary skill set for capturing time-dependent ASL changes due to exercise. We will employ imaging sequences most suited to capture anatomical and brain blood flow, lasting ~20 minutes before exercise and ~30 minutes after exercise.

**Cognitive Testing:** Evidence suggests that subtle, transient cognitive effects of exercise are detectable immediately following an acute exercise bout in older adults. We will employ a short battery of cognitive tests to capture exercise-related change in: executive control, episodic memory, and processing speed. The battery will last ~20 minutes, depending on participant speed.

Our primary cognitive measure will be the response time cost of incongruent stimuli on the Flanker Test. The Flanker Test is an executive function task that measures inhibitory control with a well-documented history of indexing change following exercise intervention (our long term goal), and early in AD.

**Aim 1: Characterize CBF change after exercise.** Our primary outcome of interest for Aim 1 is global CBF percent change from baseline from rest to immediately after exercise. Secondary outcomes will be absolute change in CBF (ml/100g tissue/min) and spatial coefficient of variation (an indirect measure of arterial transit time). We hypothesize that older participants have blunted exercise-induced change in CBF.

**Aim 1 Statistical Analyses:** Custom software utilizing the ASL Toolbox for SPM 12 will quantify global CBF. Our primary and secondary outcome measures are continuous, and thus we will use linear mixed models (LMM). We will include a random intercept coefficient to allow for each pre-post exercise pair to account for individual baseline differences. Age group will be modeled as a fixed effect. Other analysis techniques may be employed as they become available.

**Sample Size:** To our knowledge, there are currently no peer-reviewed reports of genotype-based CBF differences in response to acute exercise. However, perfusion measures in genetic risk for AD (APOE e4) have been performed previously and can form the basis of a reasonable power analyses. Thus, our sample size was determined based primarily on feasibility and preliminary data. First, KU is uniquely suited to perform this study. We have had success in recruiting and characterizing individuals for imaging and exercise studies under complex protocols. Second, two prior cross-sectional estimates of the relationship of perfusion and e4 carriage have delivered similar effect sizes ( $d=1.0$ ). Given this power, we expect to be able to discern differences between sex, and between older adults with and without cognitive impairment.

**Exploratory Aim: Describe the relationship between CBF and cognitive performance after acute exercise.** Our primary outcome will be the response time on the Eriksen Flanker Task. We will explore these cognitive effects in individuals, assessing how CBF and our blood-based biomarkers relate to cognitive improvements. These data will set the stage for future work assessing who responds to habitual exercise with cognitive improvements, and through what mechanisms.

**Exploratory Aim Statistical Analyses:** We will use the same least squares regression approach as in Aim 2.

**Data Management:** Study data will be collected and managed using the Research Electronic Data Capture (REDCap) web-based, electronic data capture tools. Imaging data will be archived and backed up on a dedicated XNAT server operated by the Hoglund Brain Imaging Center. Hoglund also maintains an imaging analysis server that provides researchers access to up-to-date imaging software (e.g. SPM). The PI has over 10 years of experience with REDCap, XNAT, and imaging analysis. Both departments ensure data security by managing all data HIPAA compliant servers that have role-based access and regular backup.

### **Participant Compensation**

Participants will be compensated \$100 after the study visit through the Greenphire Clin Card system.

### **Protection of Human Participants**

#### **a. Human Participants Involvement and Characteristics:**

For this study, we plan to enroll up to 80 participants from our screening population (the KU ADC Clinical Cohort, and Recruitment Database), other research databases on the KUMC campus (e.g. Pioneers or FitHawks with permission) and the community. Goal enrollment is:

- 1) up to 20 individuals, age 18-65
- 3) 60, age 65-85 (approximately equal APOE4 carrier and APOE4 non-carrier)

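### The APOE4 carrier split is set only for ages 65-85 and Aim 1 names age group as its only fixed effect, so a different carrier mix in the younger group could shift the age contrast modestly

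*Combined protocol and SAP*

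**What the plan says.** **Recruitment (Approach, Recruitment paragraph).** Contact starts from a list enriched to two E4 carriers per non-carrier. A co-investigator monitors carriage and asks for list changes to keep haplotypes balanced. No age range is attached to that balance. Carriers are put at about 33% of the Clinical Cohort.

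**Enrolment goals (Protection of Human Participants, item a).** The older group is "60, age 65-85 (approximately equal APOE4 carrier and APOE4 non-carrier". The younger group is "up to 20 individuals, age 18-65", with no carrier share. Sources beyond the KU ADC lists include "other research databases on the KUMC campus (e.g. Pioneers or FitHawks with permission) and the community".

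**Genotyping (Blood Draw; Potential risks, Genotype).** People without a KU ADC genotype are typed at the single study visit, when "an additional ~6mL of blood will be drawn at baseline for the purposes of genotyping". Between retrieval and new typing, genotype is obtained for everyone.

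**Aim 1 (Study Protocol).** "Our primary outcome of interest for Aim 1 is global CBF percent change from baseline". The hypothesis is about age: "We hypothesize that older participants have blunted exercise-induced change in CBF". The model has a random intercept, and "Age group will be modeled as a fixed effect". No APOE4, time or age group-by-time term is named. The paragraph ends: "Other analysis techniques may be employed as they become available".

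**Sample Size.** The plan cites d = 1.0 for cross-sectional perfusion by E4 carriage. It also says that no peer-reviewed reports exist on genotype and the CBF response to acute exercise.

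**The concern.** The design fixes the genotype mix in one of the two groups that Aim 1 compares, leaves it open in the other, and omits genotype from the model. The protocol itself treats APOE4 as related to CBF: the Significance section links the CBF aims to it, and the Sample Size paragraph argues from it. If the mix differs between age groups and carriage affects the response, part of the older-minus-younger difference is a genotype difference.

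The direction depends on two unknowns. With fewer than 50% carriers among the younger participants, an E4 effect that lowers the response adds apparent blunting, and one that raises it hides some. Above 50% both reverse. Unless carrier share is reported by age group, a reader cannot bound the shift.

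**Working it through.** The plan states no alpha, power, SD or derived sample size for the age contrast, so there is no figure to reproduce.

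**Inputs from the documents.** Enrolment goals: 20 younger and 60 older (20 + 60 = 80; the Overall Study Design paragraph gives 90). Older carrier share: about 0.50. Candidate younger shares: 0.33 (Clinical Cohort) and 0.67 (the 2:1 list).

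**Assumptions.** Two-sided 0.05; E4 effect d of 0.25, 0.5 or 1.0 within-genotype SD, equal at both ages; one percent-change value per person; no dropout; true blunting of 0.75 SD where power is given. The last is close to the difference detectable with 80% power: (1.96 + 0.84) x sqrt(1/20 + 1/60) = 2.80 x 0.258 = 0.72 SD.

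**Shift.** Older minus younger = (0.50 - p) x d, where p is the younger share and a positive d raises the response.
- p = 0.33, d = 0.5: 0.17 x 0.5 = 0.085 SD.
- p = 0.33, d = 1.0: 0.17 SD.
- p = 0.67: the same sizes with opposite sign.
- p = 0.50: zero.

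The shift does not depend on the total enrolled.

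**False positives with no age effect.** The unadjusted SE is sqrt{[1 + p(1-p)d²]/20 + [1 + 0.25d²]/60}.
- p = 0.33, d = 0.5: SE 0.2655; shift/SE = 0.32; rejection 6.2%.
- p = 0.33, d = 1.0: SE 0.2862; shift/SE = 0.59; rejection 9.1%.

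Simulation (200,000 trials per case, 30 of 60 older carriers fixed, younger carriers binomial) gives slightly lower rates:

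| E4 effect | p = 0.33 | p = 0.50 | p = 0.67 |
|---|---|---|---|
| 0.25 SD | 5.2% | 4.9% | 5.2% |
| 0.5 SD | 5.9% | 4.8% | 6.0% |
| 1.0 SD | 8.2% | 4.4% | 8.3% |

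With exactly 7 or 13 younger carriers of 20, the rate is 5-6% even at 1.0 SD. With APOE4 in the model it is about 5% in every case, given an equal E4 effect at both ages.

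**Power for 0.75 SD blunting, d = 0.5.** At p = 0.33 with E4 raising the response, the expected contrast is 0.75 - 0.085 = 0.665. Then 0.665/0.2655 - 1.96 = 0.54, or 71% (simulated 70%). With E4 lowering it, 0.835/0.2655 - 1.96 = 1.19, or 88% (simulated 88%). At p = 0.67 the two swap. At p = 0.50 it is 80%. Adjusted power is about 81% throughout.

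**Range over the assumed blunting**, same formula, p = 0.33 and d = 0.5; the adjusted SE is 0.2582 x 1.016 = 0.2623.
- 0.5 SD: 35% or 60% unadjusted (E4 raising or lowering), 48% adjusted.
- 1.0 SD: 93% or 98% unadjusted, 97% adjusted.

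**If E4 acts only in older participants (1.0 SD).** The unadjusted contrast differs from the non-carrier age contrast by 0.50 SD. The adjusted one differs by 0.36 SD at p = 0.33, 0.50 at 0.50 and 0.64 at 0.67 (simulated). Adjustment then helps, does nothing, or makes matters worse, according to the share.

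**The case against.** One reading of the Recruitment paragraph removes the problem. Overall haplotype balance, together with an even split in the older group, implies an even split in the younger group and no shift. Visit-day genotyping does not defeat this, because carriage is monitored as enrolment proceeds and later lists can be changed. This stands as a real possibility. But the text gives that balance no age scope, the numeric goal is stated for ages 65-85 only, and people typed at the visit cannot be chosen on genotype beforehand. What is firmly shown is an ambiguity.

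The size is also small. At 0.25 or 0.5 SD the false-positive rate barely moves, and the cited d = 1.0 concerns resting perfusion, not percent change after exercise. This stands too, and it limits the grade.

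The closing sentence of the Aim 1 analysis paragraph would permit adjustment. Permission is not prespecification: it leaves the choice of whether to adjust until after the data are seen.

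Finally, adjustment removes only the genotype-mix part of a non-randomised age comparison, and it assumes a similar E4 effect at both ages. Both points are correct, and the second is why a sensitivity analysis is needed.

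**Conclusion.** The point holds as a modest, conditional improvement. The omission is plain in the text; the size of its effect is not known. On the two shares that the documents allow one to try, the shift is 0.085 SD for a 0.5 SD effect and 0.17 SD for 1.0 SD. The effect size, the application of those shares to the younger group, the 20 v 60 split, two-sided 0.05, the 0.75 SD blunting and the equal E4 effect across ages are all assumptions.

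A reader might infer that the Aim 1 contrast is biased, or biased towards the blunting hypothesis. The documents do not support that: they give neither the younger share nor the effect on the response, and either unknown can reverse the sign or make the shift zero. Nor do they support treating d = 1.0 as the expected effect on CBF change. And adjustment is not a guaranteed cure, since it can fail to help if E4 acts differently by age.

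**What to change.** 1. In Aim 1 Statistical Analyses, prespecify APOE4 carriage (yes/no) as a covariate for percent change. If pre and post CBF values are modelled instead, name age group-by-time and genotype-by-time, since neither is there now.
2. Report carrier share by age group.
3. State in Recruitment or in the enrolment goals whether the haplotype balance covers ages 18-65.
4. Give the age contrast in non-carriers as a sensitivity analysis, labelled as lower-powered. For 0.75 SD its power is about 60%, 51% and 39% at younger shares of 33%, 50% and 67% (about 13, 10 and 7 younger non-carriers v 30 older).

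The cost is wording, because genotype is already obtained for every participant. The model loses one degree of freedom (one or two in a pre/post model). If APOE4 has no effect, power for 0.75 SD falls from about 82% to about 81% at younger shares of 33-67%.

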### **Inclusion Criteria:**

- Age 18-85 (inclusive)
- English speaking
- Normal or corrected hearing or vision,

### **Exclusion Criteria:**

- Cognitive impairment (adjudication can include CDR>0 or QDRS equivalent in last 6 months) unless under age 50 for which cognitive adjudication by above means is not necessary).
- Clinically significant cognitive or psychiatric illness, or other neurological disorders that have the potential to impair cognition (e.g., Parkinson's disease, stroke defined as a clinical episode with neuroimaging evidence in an appropriate area to explain the symptoms).
- Myocardial infarction or symptoms of coronary artery disease (e.g. angina) in the last 2 years.
- ACSM Cardiac Risk stratification of High Risk, unless confirmation of doctor that moderate exercise is appropriate.
- Significant pain, metabolic, or musculoskeletal disorder that would contraindicate exercise.
- MRI exclusions or claustrophobia
- Any clinician prescribed activity restrictions unless clearance is obtained for study
- Anti-coagulant use

**b. Sources of Materials:**

Description of research materials: Magnetic resonance images, blood/genotype, and cognitive performance will be the only material collected for analyses. Health information such as health/medical history, medication, and medical records will be collected with consent. Participant data will be coded, and only the study team will have access to the codes. All data will be collected for this research study under conditions approved by the KUMC IRB.

Management, analysis and protection of materials, including data management plan: The study will be submitted for review to the KUMC IRB, and will be conducted in accordance with Good Clinical Practice and HIPPA guidelines. Participants will provide written informed consent prior to entering the study. All identifiable files, data, and tissue will be coded and stored in secure locations. The PI will be responsible for the quality of the data and will supervise the data acquisition with the help of the study team. The REDCap database system uses data validation and review algorithms to support data quality. There is no billing of participants, their families, or third party payers for the research assessments.

**c. Potential risks:**

**Moderate-Intensity Exercise:** Potential risks of the exercise stimulus as well as the exercise intervention include unpredictable changes in blood pressure or heart rhythm, myocardial infarction and death as well as the less serious problems of fatigue, muscle soreness, tripping, falling, and other injury to tendons, ligaments, joints, and muscles. This protocol requires effort well below maximal and is within standard exercise prescription for healthy adults. Risk is minimized by our Exclusion Criteria which preclude enrollment of individuals at risk for cardiac or orthopedic complications. There is no statistical information regarding serious complications during exercise testing in patients without ischemic coronary heart disease. A review of the experience of 30 cardiac rehabilitation programs reported information on 13,750 participants who accumulated 1,629,634 patient hours of supervised exercise. A total of 50 cardiac arrests were observed, 42 of which were successfully resuscitated while 8 were fatal. Events are extremely rare, and participants will be screened for risk of cardiovascular disease and symptoms. Emergency equipment, including defibrillator, and ambulance plan are available for all participants.

**Neuroimaging:** MRI scanning is not generally associated with any health risks. Trained technicians at the Hoglund Brain Imaging Center thoroughly screen all individuals before scans. Claustrophobia and non-compatible implanted devices are listed as exclusion criteria. The confined space and loud noise can be uncomfortable. The study team will prepare the imaging table in advance and provide ear plugs to ensure comfort. **Blood draw:** Routine risks involving laboratory testing include minor pain, bruising, and swelling at the needle site, discomfort of hunger or thirst due to fasting. Less likely is the possibility of lightheadedness, or even briefly feeling faint during the blood drawing procedure.

**Genotype.** APOE e4 genotype data will be requested from the KU ADC (HSC #11132) for subjects who participate in the KU ADC Clinical Cohort or other studies that share this information back to the Clinical Cohort, and will be generated from all other participants. In some instances, we will also generate the genotype as part of this study. There is potential negative impact if this information were to become known. Thus, this

information will be stored electronically in a secure password protected REDCap database and any paper copies of records will be filed by number in accordance with professional standards of privileged information in a secure badge-access file room at the KU CRC.

**Adverse Events:** Adverse events are defined as any untoward medical occurrence in study participants or others, which does not necessarily have to be a causal relationship with the study treatment. The seriousness of the adverse event will be determined using the National Cancer Institute Common Terminology Criteria for Adverse Events (CTCAE) v3.0, and any adverse event requiring hospital admission. Adverse events will be assessed only at the visit, but the consent form will have contact information should the participant need to contact the study team regarding delayed development of an AE. Serious Adverse Events will be reported per KUMC requirements.

Safety of the study will be monitored in an ongoing manner by a DSMC according to the DSMC charter and Independent Safety Officer according to a Safety Plan.

### **Adequacy of Protection Against Risk**

**a. Recruitment and Informed Consent:** Recruitment occurs by referrals from organizations serving large numbers of older adults, public service announcements through media, physician referral, other KUMC recruitment sources, and word of mouth. We will also recruit from our pre-existing ADC cohort of participants who have previously given consent to be contacted for future studies. We are very sensitive to issues related to the participant's ability to understand the elements of consent and their capacity to make decisions. We employ a "teach-back" method to confirm understanding of the procedures. Initial screening consent will be acquired verbally over the phone. Written informed consent will be obtained by the PI and/or designated staff for the visit procedures, and the purposes of the study, its assessment procedures, and risks and benefits will be explained. The original signed consent form is kept with the participant's confidential file and a copy is given to the participant.

**b. Protection Against Risk:** All research data are maintained confidentially in password-protected databases. All paper copies are filed by number in accordance with professional standards of privileged information. Confidentiality is strictly safeguarded by HIPAA-compliant standards.

Additionally, the following policies will be adopted to assure the safety of the participants in this study:

1. Strict adherence to institutional regulations for conducting clinical research
2. The involved support staff will be adequately trained to conduct human research and will have completed the necessary institutional web-based training prior to the study
3. We will comply with HIPPA regulation and commit to maintaining the patient confidentiality.
4. Any research presentations or publications from the proposed studies will not disclose any personal identity information.

